Aim 2a: Determine the effect of early combined EN + PN on intestinal barrier function in children with AHRF.

Aim 2b: Identify patient, disease, and treatment factors, which act as effect modifiers for non-invasive markers of intestinal barrier function for children with AHRF.

Aim 2c: (Exploratory) Determine the influence of EN +/- PN on the intestinal microbiome in children with AHRF.

This proposal is innovative, because will evaluate the extent to which early combined enteral and parenteral nutrition improves delivery of daily and cumulative goal calories, protein, and indices of nutrition (Aim 1), while monitoring for potential negative consequences of early PN on intestinal barrier function (Aim 2). *This proposal is significant*, because it is expected to improve our understanding of optimal timing for parenteral nutritional support and define the effect of route and dose of nutrition, patient, disease, and treatment characteristics on intestinal barrier function. By understanding how patient, disease, and treatment factors impact intestinal barrier function during pediatric AHRF, we may be able individualize dose of enteral nutrition to protect against gut barrier dysfunction and promote new strategies to reduce septic morbidity; meeting the goals of NIH Healthy People 2020.

Timeline of Interventions

Screening and Eligibility

Screening is to take place twice daily (~8am and ~5pm) for newly intubated patients that meet inclusion criteria. All screened patients will receive a study ID. Enter the patient on the SUPPER Enrollment log for study ID. Complete the SUPPER Screening form for all screened patients. If the patient does not meet eligibility, complete the SUPPER Enrollment log and the Supper Screening form and place the Screening form in the study binder under Completed Screenings. If the patient meets all inclusion criteria, with no exclusion criteria, the patient is eligible and the family may be approached for consent. If unsure whether an individual patient can be enrolled in the SUPPER study, please call the University of Arizona PI.

Inclusion Criteria-

Intent: To identify PICU patients who have Acute Hypoxemic Respiratory Failure and who will receive early enteral feeding.

Inclusion Criteria

1. Admitted to study hospital pediatric intensive care unit (PICU),
2. One month to 16 years of age,
3. Exhibits Acute Hypoxemic Respiratory Failure as defined as:

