Patients ≥ 8 years of age are to be approached for assent if the patient is extubated, no longer under the influence of sedatives and analgesics, and the patient is actively receiving early or late parenteral nutrition per study. If no assent obtained because the patient is sedated and unable to participate in the assent process, document this on the assent form and keep in patient study file. If the child does not provide assent once able to cooperate with assent, the intervention is discontinued at that point. All data obtained prior to assent will be utilized. File original assent forms with original parental

consent form in the patient study file and document assent on the SUPPER Enrollment form. Make two copies of the assent form, one for the family and one for bedside.

Randomization

Randomization takes place within 48 hours of PICU admission or initiation of mechanical ventilation. Patients are blocked randomized by age and pre-existing acute or chronic malnutrition (based on admission weight for age BMI z score) to either early or late parenteral nutrition (PN) supplementation. There are 9 randomization stratifications (see table below). Randomization cards are pre-generated; random sequence was created using a random generator with atmospheric noise at random.org. BMI z-score is derived from one of two websites. If <2 years of age, use www.emmes.cpm/study/ped/resources/htwtcalc.htm; if ≥2 years of age, use www.stokes.chop.edu/web/zscore/index/php.

	1month to <3 years	3-10 years of age	11-16 years of age
BMI z score < -1 and >-2 (Low)	A1	B1	C1
BMI z score -1 to +1 (Normal)	A2	B2	C2
BMI z score > +1 and < +2 (High)	A3	B3	C3

To randomize a successfully consented patient, use age and BMI z score to determine which randomization block the patient should be in. Choose the first randomization envelope in the pack. The envelope will have a card stating the intervention arm. Record the patient's study ID, patient age, BMI z-score, name of study personnel randomizing, and date/time of randomization on the card, and staple to the SUPPER Screening Form. Document date, time and study intervention randomized on the patient's SUPPER Screening form and SUPPER Enrollment Log.

Once randomized, email the study PI the patient's study ID, age BMI z score, date and time of randomization, and assigned intervention.

Patient Kits and Supplies

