If an adverse event occurs, it is to be noted on the SUPPER Adverse Event Log and the SUPPER Daily Data Collection form for the day the event occurred. All adverse events will be reviewed weekly by [name] to ensure study patient safety.

Report A/E and SAE per local IRB regulations as needed and required.

Data and Safety Monitoring Plan

Should study subjects have adverse events related to study interventions in Aim 1 or Aim 2 we will report these to the local and primary IRB and the Safety Officer ([name]). The DCMC study coordinator will produce Administrative Reports quarterly to describe study progress to include: accrual, subject demographics, and subject status. Reports will also describe adherence to inclusion/exclusion criteria, and protocol deviations. Safety reports will also be generated quarterly, or if enrollment exceeds expectations, at least with every 10 patients enrolled, list frequencies of adverse events, serious adverse events, safety outcomes, deaths, and disease or treatment specific events in blinded groups for review. These reports will be reviewed internally for ongoing quality control and then presented to the Safety Officer, DSMB, and IRB. The Safety Officer will review these quarterly reports to ensure good clinical care and identify any potential trends. The Safety Officer may request interim reports and analysis between meetings or prior to the scheduled interim analysis when necessary. Clinicians will be blinded to the safety monitoring data, as exposure to emerging trends may influence enrollment and care, biasing the study. This is designed as a single-blinded study so that the treating physician and investigative team are aware of group assignment in the event of electrolyte abnormalities, loss of central venous access, and related to feasibility of blinding PN. Our safety officer will also review charts for randomized subjects to ensure that no adverse events are attributable to the study intervention, this is in addition to review by the study PI.

Interim Safety Analysis

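### The randomization card is linked to the child only after the arm is seen, with no pre-opening record or planned reconciliation described, so allocation concealment is not assured

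*Combined protocol and SAP*

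**What the plan says.** The Randomization section gives the steps in order. Staff place the child in one of nine strata (three age bands by three BMI z bands), taking the z score from one of two websites. Then: "Choose the first randomization envelope in the pack. The envelope will have a card stating the intervention arm". Next: "Record the patient's study ID, patient age, BMI z-score, name of study personnel randomizing, and date/time of randomization on the card". The card is stapled to the Screening Form. After that: "Document date, time and study intervention randomized on the patient's SUPPER Screening form and SUPPER Enrollment Log". Last: "Once randomized, email the study PI the patient's study ID, age BMI z score, date and time of randomization, and assigned intervention".

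Before any envelope is drawn, Screening and Eligibility provides that "All screened patients will receive a study ID", with a Screening form and an Enrollment Log entry. Consent and Assent adds the consent record.

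The cards are pre-generated from a random sequence. The section says "Patients are blocked randomized by age and pre-existing acute or chronic malnutrition", but gives no block size or allocation ratio. The Data and Safety Monitoring Plan calls the trial single-blind and explains that "the treating physician and investigative team are aware of group assignment".

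The manual does not say whether envelopes are sealed, opaque or numbered, whether cards carry a stratum label, who holds the packs and the generated list, or whether used cards are compared with that list.

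**The concern.** Allocation concealment depends on committing a child to the next assignment before anyone can see it. Here the commitment comes after the arm is visible. Someone who would prefer the other arm for a particular child could put the card back and take the next one, or take one from another stratum's pack. The paperwork would then be completed for the arm finally chosen.

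The manual itself names possible reasons for a preference. The early PN section discusses fluid overload and PN the clinical team judges unsafe to continue. The Interim Safety Analysis lists hospital-acquired infection, dialysis, longer ventilation and death as outcomes to watch. If children were steered on severity that is not fully measured, the comparisons between arms in Aims 1 and 2 could be biased, and a sample of about 40 leaves little room for adjustment.

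**Working it through.** The plan gives no figure to reproduce. The check is mainly of the order of steps.

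**1. What exists before and after the arm is seen**

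- Before: study ID, Screening form, Enrollment Log entry and consent. None is tied to an envelope. The forms are not part of the documents, so it cannot be told whether age and z score are already entered at screening. If they are, that would point to a stratum but still not to an envelope.
- After: the details on the card, because the card is inside the envelope and states the arm; the Screening form and Log entries, because they report the arm; and the PI email, for the same reason. The listed content of the email includes neither an envelope number nor a stratum label.

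**2. Whether another section supplies a check**

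- Protocol Deviations has six categories. None concerns randomization; only the residual category Other could hold it.
- The quarterly reports cover accrual, demographics, subject status, eligibility adherence and deviations, plus safety. They do not cover allocation order.
- Enrollment Log data go into REDCap weekly, so the database gives no pre-allocation time stamp.

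**3. What a later comparison could find, if the generated list was kept in pack order**

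- Redraw within a pack: it changes the assignment only if the two cards differ, and then the order of arms departs from the list (for example, generated early then late, used late then early). Detectable.
- Draw from another pack: the recorded age and z score point to one stratum while the arm came from another, so the stratum falls out of step with its list. Detectable.
- A z score near -1 or +1 altered before it is written down: card and pack agree. Only recalculation from source measurements would show it, and only children near a cut-point are affected.
- BMI z of -2 or below, or +2 or above: the stratum table has no row and no exclusion criterion removes these children, so there is no expected pack to compare with.

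**4. What one redraw gains (illustration)**

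Assume 1:1 allocation. Let q be the chance that the second card differs from the first. The chance that at least one of two cards shows the preferred arm is 0.5 + 0.5q.

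- Simple random list: q = 0.50, so 0.5 + 0.25 = 0.75.
- Permuted blocks of size b, at the start of a block: q = (b/2)/(b-1).
  - b = 2: q = 1.00, giving 1.00.
  - b = 4: q = 2/3 = 0.67, giving 0.83.
  - b = 6: q = 3/5 = 0.60, giving 0.80.

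Without a redraw the chance is 0.50. The Aim 2 analysis text counts on 40 subjects, so each redirected child is 1/40 = 2.5% of assignments.

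**5. Predictability is a separate matter**

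If permuted 1:1 blocks of size 2m are assumed, the share of allocations fixed by earlier cards is at most 1/(m+1): 50%, 33% or 25% for sizes 2, 4 or 6. These are complete-block upper limits. A simulation with 40 children in nine equally likely strata gives about 44%, 24% and 12% with one set of packs, and 39%, 14% and 3% with separate packs at two sites.

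**The case against.** The strongest reply is that the procedure leaves a substantial trail. Age, z score, time, arm and the name of the person randomizing are recorded, and most of this also goes to the PI by email. The sequence was generated in advance, there is a take-the-first rule, and the child is registered and consented before the draw. All of that stands. A reader might infer that a redraw would be untraceable; the documents do not support that, because step 3 shows that most routes could be found afterwards. What remains is that every record linking a child to an assignment is made with the arm known, and that nobody is assigned to make the comparison.

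A reader might also infer that the envelopes are unsealed or unnumbered and that allocation is unprotected. The manual is silent on these points, and silence is not evidence of absence. Nor is the trial described as open: it is labelled single-blind, and the supported statement is that the treating and investigative teams know the arm. The manual has study personnel randomize; it does not say that bedside clinicians draw the envelopes.

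Finally, block-tail prediction is not established. The section uses the word block for the age and z-score cell itself, so blocked may mean only stratified. With a simple random list in each stratum, earlier cards predict nothing. The figures in step 5 therefore cannot be used as the size of this concern.

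**Conclusion.** The concern holds as a gap in the written procedure. The card is tied to the child only after the arm is seen, and no pre-opening log, envelope number or reconciliation is described. A redraw or a draw from another stratum's pack is therefore not prevented and would not be found by any planned check, though a later comparison with the generated sequence could reveal most cases. Concealment is not assured. It would go beyond the documents to say that it failed, or that anyone acted improperly.

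The size of any bias cannot be estimated. What can be said is that one redraw raises the chance of a preferred arm from 0.50 to 0.75 under a simple 1:1 list, or to between 0.80 and 1.00 at the start of an assumed permuted block of 6 to 2. The ratio, the block structure and a planned total of 40 are assumptions here; the manual also places an interim safety review after 40 enrolled, so the final total could differ.

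**What to change.** Reverse the order of the existing steps:

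1. Before opening, write the study ID, age, BMI z score, stratum and date/time on the next sealed, sequentially numbered envelope for that stratum.
2. Send the existing PI email at that point, with the stratum and envelope number added.
3. Open the envelope and report the arm in a reply to the same email.
4. Keep the envelope with the card.
5. At each quarterly report, reconcile envelope numbers and arms against the Enrollment Log and the generated sequence, preferably by someone who does not enroll patients.

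The stratum table should also say which pack applies to z scores beyond its range, or that such children are not randomized, so that the reconciliation has an expected stratum for every child. The DSMB section describes the study as ongoing, so the change can apply to the remaining envelopes. The cards already stapled to Screening Forms can be checked once against the generated sequence if it was kept.

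The cost is a change to the manual, numbering of the remaining envelopes, a minute or two before opening, a second short email, and one reconciliation step per quarter. Staff and data fields stay the same. The change makes redraws and pack switching hard to carry out unnoticed. It does not remove any predictability that comes from blocking.

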To assess 28 Day Vitals first check to see if the patient is still hospitalized or if the patient died while hospitalized. If patient is not hospitalized, use the SUPPER Contact form to contact the patient's parents/guardians. Three attempts should be made to contact the parents/guardians. If the third attempt is unsuccessful, attempt to contact the patient's primary care physician. If the patient has not

been seen by the primary care physician since hospitalization, assess vital status from county death records. If you can successful contact either the patient's parents/guardians or primary care physician obtain information on whether the patient's condition is better, the same, or worse from condition at discharge. Also obtain information on whether the patient was readmitted to the hospital on or before 28 Days.

Late Parenteral Nutrition Supplementation (LPN)

Supplies and forms for have on hand after randomization.

SUPPER Tablet with SUPPER Titration

SUPPER Patient Study Binder

SUPPER Sample Kit

Tape measure to measure mid upper arm circumference

Once randomized to Late Parenteral Nutrition (LPN), patients are to be started on EN within 2 hours of randomization if not already started. Patients randomized to LPN will receive enteral nutrition for 168 hours and supplemental PN if not reaching 80% goal feeds starting at Hour 96 for a total of 72 hours. Calorie goal and titration of feeds are according to the SUPPER Titration. Obtain mid upper arm circumference.

Prior to LPN Hour 0, set up SUPPER Tablet at bedside. Open the SUPPER Titration and enter all of the patient demographics, formula, and fluid information at the top. Rates for EN and remaining fluids will populate. Print SUPPER Titration for bedside and study binder and review with the bedside nurse.

The SUPPER Titration uses Schofield's equation to calculate the initial kcal/day goal. Patients are to initially receive a max of 75% of calorie goal and 1.5gm/kg/day protein for the first 24 hours. Patients will receive 100-120% of MREE and 2-3gm/kg/day protein with combined EN by study day 2, not to exceed 1600mL/M²/day in fluids. As the patient can tolerate, EN is to be escalated every 4 hours to full kcal/day goal.

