Prior to patient PICU discharge, complete the SUPPER Contact Form with the parent/guardian that provided consent for this study. This form will be used for the 28 Day Vitals check if patient is not in the hospital or deceased.

There are 5 key sections to the SUPPER Discharge Form, Extubation, PICU Discharge, Hospital Discharge, Early Cessation, and 28 Day Vitals and Patient Death. Complete each of these sections as they occur.

To assess 28 Day Vitals, first check to see if the patient is still hospitalized or if the patient died while hospitalized. If patient is not hospitalized, use the SUPPER Contact Form to contact the patient's parents/guardians. Three attempts should be made to contact the parents/guardians. If the third attempt is unsuccessful, attempt to contact the patient's primary care physician. If the patient has not been seen by the primary care physician since hospitalization, assess vital status from county death records. If you can successful contact either the patient's parents/guardians or primary care physician obtain information on whether the patient's condition is better, the same, or worse from condition at

discharge. Also obtain information on whether the patient was readmitted to the hospital on or before 28 Days.

Subject Withdrawal

Subjects may withdraw from the study at any time. Should the patient or the patient's parents/guardians wish to withdraw, note the date, time, and reason for withdrawal on the SUPPER Discharge Form. If the patient is receiving supplemental PN when they wish to withdraw from the study, review the risks associated with abrupt discontinuation of PN, and advise that the patient will require blood sugar monitored 2-3 times over a 24 hour period to ensure they do not develop hypoglycemia. Ask parents/guardians if we may continue to collect information from the medical record without continuing any study procedures for outcome analysis. If they gave permission to bank samples for future research, ensure this has not changed.

Data Collection and Entry into REDCap

Prior to starting the study, sites will provide a written plan on how and from what system data is obtained. This is to assist with consistency of source of information, and to provide a guide for data monitoring. For instance, if vitals and medications are found in different applications of the medical record system, it should be noted where source documentation is obtained.

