The study subjects are mechanically ventilated, critically ill infants and children with acute respiratory failure and as such are known to have mortality rates of 8-22%. We do not anticipate any serious adverse events specifically related to the short-term use of study PN formulations, performance of the metabolic cart, or to blood and urine sampling, but will report standard adverse events. All serious, unexpected, or unanticipated problems that are potentially related to study procedures will be reported to the PI, local IRB, the medical monitor, the DSMB and study sponsor within 24 hours. SAE's and AE's will be reported up to and including 14 days after study enrollment. Ongoing SAE's and AE's will be followed until resolved. A 28-day AE, SAE follow up form will be included in subject monitoring for 28-day vital status. The medical monitor will determine if the serious adverse event is potentially related to study procedures.

For safety monitoring, all adverse and serious adverse events are to be recorded and tracked. In addition to local site reporting for adverse events and serious adverse events, following guidelines are to be followed for this study.

Serious Adverse Event is any of the events listed below:

1. Death within 28 days of enrollment
2. Cardiopulmonary arrest
3. Operation or re-operation
4. Any other event that is not listed in the Expected Adverse Events, that increased risk and/or harm to the patient, may increase hospital length of stay, or require treatment.

If one of these events occurs, the medical monitor and PI within 24 hours of knowledge of the event. These events are also recorded on the SUPPER Adverse Event Log. A chart review of events leading up to the SAE will be required to determine relatedness to the study.

Expected Adverse Events

1. Aspiration of tube feeding
2. Unplanned extubation or need for reintubation
3. Pneumothorax
4. Desaturation < 85%
5. Pulmonary embolus
6. Catheter associated thrombosis
7. Healthcare acquired infections (Catheter associated blood stream infection, ventilator associated pneumonia, catheter associated urinary tract infection) as defined by the hospital infection prevention
8. Readmission to the pediatric intensive care unit
9. Cholestatic jaundice
10. Hyperglycemia (blood glucose >250 mg/dL)
11. Hypoglycemia (blood glucose <60 mg/dL)
12. Hyperammonemia
13. Acute Kidney Failure

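### In the 28-day status check, an early primary-care visit bypasses the death-record search, so a later death may be missed

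*Combined protocol and SAP*

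**What the plan says.** The 28-day vital status check appears twice, under Discharge and Follow Up in the early PN (EPN) section and again in the late PN (LPN) section. The steps are the same in both:

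1. Staff "first check to see if the patient is still hospitalized or if the patient died while hospitalized".
2. If the child is out of hospital, the family is contacted: "Three attempts should be made to contact the parents/guardians".
3. "If the third attempt is unsuccessful, attempt to contact the patient's primary care physician".
4. "If the patient has not been seen by the primary care physician since hospitalization, assess vital status from county death records". The EPN section has the same last step: "been seen by the primary care physician since hospitalization, assess vital status from county death records".

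Whoever is reached, parent or physician, is asked how the child's condition compares with that at discharge. A further instruction reads: "Also obtain information on whether the patient was readmitted to the hospital on or before 28 Days".

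The adverse event definitions list "Death within 28 days of enrollment" as the first serious adverse event. Routine event reporting runs to 14 days after enrollment, and "A 28-day AE, SAE follow up form will be included in subject monitoring for 28-day vital status". The Interim Safety Analysis section names mortality among the outcomes that can lead an independent panel to ask for unblinded data and, in the end, to stop Aim 1.

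Neither the follow-up text nor the Statistical Analysis Plan gives a rule for a child whose 28-day status is unknown.

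**The concern.** The last step depends on the wrong condition. The check needs to know whether any source can vouch for the child up to day 28. The rule asks only whether the physician has seen the child at all since the hospital stay, and it sets no earliest date for that visit. Staff who follow it exactly would not search death records for a child seen a few days after discharge, even if nobody has information on the following weeks.

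For a death after discharge, the records search is the only step that does not rely on a parent or physician knowing of the death and being reached. The rule drops it for children whose families have already failed to respond three times.

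At stake is the completeness of a listed serious adverse event. For a discharged child, the 28-day check is the only described procedure that actively looks for new events between day 15 and day 28, and an early visit can leave those days uncovered. The trial is small, so a single death weighs heavily in an arm's mortality.

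**Working it through.** The plan states no figure on this point, so there is nothing to reproduce. The check has two parts.

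**Logic of the trigger.** Take an invented record: discharge on day 10, one physician visit on day 13, and a family that cannot be reached.

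- Has the physician seen the child since the hospital stay? Yes, so the condition for the records search is not met.
- Does the visit show status at day 28? No. The visit leaves days 14 to 28 uncovered, which is 28 − 13 = 15 of the 28 − 10 = 18 days after discharge.
- Does any other sentence require the physician's information to reach day 28? For vital status, no. The readmission question covers the whole window, but it does not date the physician's knowledge.

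A death on, say, day 20 is then found only if the physician happens to know of it.

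**Scale.** From the documents: N = 40 (Statistical Analysis Plan) and mortality of 8–22% (adverse event definitions). Equal arms of 20 are an assumption.

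- Expected deaths from all causes: 40 × 0.08 = 3.2 to 40 × 0.22 = 8.8 in total, or 1.6 to 4.4 per arm of 20.
- One death in an arm of 20: 1/20 = 5 percentage points.

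These totals show only how much one death weighs. They do not measure the gap, because status in hospital is checked first.

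Expected missed deaths = N × u × q × m. None of these three inputs is in the documents, so ranges are assumed:

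- u, the share of children whose status rests only on a physician whose last visit was before day 28: 5–20%
- q, the risk of death between that visit and day 28: 1–5%
- m, the chance that the physician does not know of the death: 50–100%

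| u | q | m | Expected missed deaths, 40 × u × q × m | Chance of at least one, 1 − (1 − uqm)^40 |
|---|---|---|---|---|
| 0.05 | 0.01 | 0.5 | 0.01 | 1% |
| 0.10 | 0.03 | 1 | 0.12 | 11% |
| 0.20 | 0.05 | 1 | 0.40 | 33% |

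The expected number stays below one throughout. It scales with N: the highest row gives 0.20 × 0.05 × 1 = 0.01 per child, so about 100 children would be needed to expect one missed death even there.

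**The case against.** The strongest reply is that the gap is narrow. The child must be out of hospital, the family must not be reached, the physician must be reached, and the last visit must be early. A death must then follow that the physician has not heard of. Physicians often learn of such events without a further visit. All of this stands, and it is why the effect is small. It does not make the trigger correct.

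Three stronger readings are tempting, and the documents support none of them.

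- *Later events are counted as not having happened.* The text says whom to contact. It does not say that status at the last visit is carried forward, or that unknown is coded as no event. The Discharge Form is named but not reproduced, so it may have an entry for unknown status. The Statistical Analysis Plan specifies no 28-day mortality or readmission table and no denominator, so no bias in such a proportion can be derived.
- *Readmission is undercounted because of this trigger.* The question to parents or physician covers the full window, and county death records could not supply readmission in any case. For readmission, the gap is only that no rule covers incomplete information.
- *The comparison between arms is biased.* The procedure is the same in both arms, so no difference is built in.

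The arm size is also uncertain. The Statistical Analysis Plan works with 40 subjects, while the Interim Safety Analysis is set after 40 are enrolled and speaks of stopping before enrollment is complete.

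**Conclusion.** The point holds in a limited form and is minor. As written in both arms, a primary-care visit at any time after the hospital stay removes the death-record search, so a death after that visit and before day 28 may go undetected if the physician does not know of it. This is a stated rule with the wrong condition, not merely a missing detail. The likely effect is well under one missed death in 40 patients, though the chance of at least one reaches about a third at the top of the range. Both figures rest on assumed values for u, q and m. The case for a change is that the event is a listed serious adverse event, that one death is 5 percentage points in an assumed arm of 20, and that the correction is cheap.

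**What to change.** In both Discharge and Follow Up sections, replace the condition for the records search: search county death records whenever neither the parents or guardians nor the primary care physician can confirm the child's status on or after day 28. This wording also covers a physician who cannot be reached, a case the present sentence leaves unclear.

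Add a field for the date last known alive. Record readmission as unknown when no source covers the period to day 28.

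The cost is one sentence in two places, one date field, a few more searches of a kind already in the procedure, and a few children with readmission recorded as unknown. A county search can miss a death registered elsewhere, so the change narrows the gap without closing it. The date field shows how far each child was actually followed. Treatment, sample size and analysis models do not change.
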